8.4 Consented tracer condition population

Inclusion criteria:

- Aged 0-15 (<16) years
 - Age at date of consent
- Registered with a Southwark or Lambeth GP practice included in the trial.
 - Registration at time of consent
- Parental informed consent confirmed

➤ Randomised consented population

Intervention and control only, *excluding* pilot clusters

Subpopulations:

- Asthma
- Eczema
- Constipation

➤ Quasi-experimental consented population

Intervention, control *and* pilot clusters

Subpopulations:

- Asthma
- Eczema
- Constipation

Note: Self-report of tracer condition by parent/carer/CYP is acceptable. We will not confirm these against primary care data.

8.5 Consented tracer condition population where Health Check shows clinical need

Purpose: Study impact of intervention on those meeting criteria for CYPHP clinical service

Inclusion criteria:

- Aged 0-15 (<16) years
 - Age at date of consent
- Registered with a Southwark or Lambeth GP practice included in the trial.
 - Registration at time of consent
- Parental informed consent confirmed
- Completed a Health Check, and Health Check results meet or exceed threshold for clinical need. See Appendix.

➤ Randomised consented in clinical need population

Intervention and control only, *excluding* pilot clusters

Subpopulations:

- Asthma
- Eczema
- Constipation

➤ Quasi-experimental consented in clinical need population

Intervention, control *and* pilot clusters

[figure not shown]
Subpopulations:

- Asthma
- Eczema
- Constipation

Note (as above): Self-report of tracer condition by parent/carer/CYP is acceptable. We will not confirm these against primary care data.

8.6 Flow diagram and summary of reasons for leaving the cohort

Figure 1: Example flow diagram of patients included in the analysis

Summary of reasons for leaving the cohort for Health Service Use Populations

Separately from the diagram above, we may report numbers of children exiting the trial population before the end of the trial period, by arm, and the reason (e.g. 16th birthday, no longer registered with a participating GP practice).

9. LISTING OF OUTCOME MEASURES

This section lists outcome measures. They are defined in detail in subsequent sections.

9.1 Primary and secondary health service use

Activity data collected on all CYP's contacts with the health care system

1. **Non-elective admission rates (Primary outcome)**
2. Primary care consultation rates
3. Primary care outpatient appointment referrals
 - a. All
 - b. Referrals relating to tracer conditions
4. Emergency department attendance
5. Outpatient appointment attendances
 - a. All
 - b. Appointments relating to tracer conditions
6. Ambulatory care sensitive admissions
7. Proportion of non-elective admissions that are ambulatory care sensitive
8. Rate (sum per patient-year) of non-elective admissions and outpatient appointment attendances, combined

9.2 CYP physical and mental health outcomes (Consenting patients)

These will be measured as part of the CYPHP clinical service at baseline, and asked independently to the clinical service at follow-up.

9. Mental health and wellbeing using the Strengths and Difficulties Questionnaire (SDQ) (all patients)
10. Asthma severity using the Asthma Control test (Asthma patients)
11. Constipation severity as measured by CYPHP Constipation Score (Constipation patients)
12. Eczema severity using the Patient Oriented Eczema Measure (Eczema patients)

9.3 CYP health-related quality of life and parental well-being outcomes (Consenting patients)

Quality of life and well-being will be derived from parent responses to the following questionnaires (measured via patient portal after informed consent).

13. **PedsQL (Primary Child Outcome)**
14. CHU-9D – Estimates of quality adjusted life years (QALYs) the Child Health Utility

Parental mental wellbeing measures will be derived from parent responses to the following questionnaires (measured via patient portal after informed consent)

15. **Warwick Edinburgh Mental Wellbeing scale (main carer) (Primary Parent Outcome)**
16. A School & Work Absence questionnaire

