3. TRIAL EVALUATION OVERVIEW

This evaluation will address the above objectives using data about children aged 0-15 years (<16) registered with a GP practice in Southwark or Lambeth. The evaluation will take 3 levels.

1. A population evaluation (all children)
2. A tracer condition evaluation (all children identified as having or potentially having asthma, eczema, constipation)
3. a) A consented tracer condition evaluation (all children with asthma, eczema, or constipation who have consented for additional data collection and associated data linkage)
b) A consented tracer condition evaluation (all children with asthma, eczema, or constipation who have consented for additional data collection and associated data linkage) including only those who met the threshold to be offered CYPHP service(s).

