11.9 Analysis Methods

Analysis (for 6-month and 12-month follow-up): Random-effects regression models. Covariates at individual level: participant age group, sex, IMD 2015 quintile, IDACI 2015 quintile, Borough, and the baseline questionnaire outcome score. Covariates at cluster level: mean IMD 2015, mean IDACI 2015, number of children under 16 years, rate of paediatric OP referrals 2015-16, and the mean baseline questionnaire outcome score.

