11.10 Intracluster correlation and regression models

Above we have described planned random-effects regression models, to account for clustering by randomised GP cluster. However, when we observe minimal correlation within clusters, these models are not appropriate, and we will report results from standard regression models, controlling for both the individual-level and cluster-level covariates described above.

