15. EQUITY OF OUTCOMES ANALYSES

Some interventions, although they are beneficial overall, can widen inequality gaps. CYPHP aims to reduce inequality gaps.

Objective: To examine the impact of the CYPHP model of care on gradients (or variation) in health service use, physical and mental health, condition symptoms, health-related quality of life, parental well-being, and school/work absence.

To determine the impact of CYPHP on inequality gaps, we will examine differential intervention (moderator) effects, by adding an interaction term between measures of social disadvantage (listed below) and the study arm (intervention/control) variable, to the models estimating the impact of CYPHP on the study outcomes (listed below).

Measures of social disadvantage:

- IMD quintile (treated as ordered categorical variable)
- IDACI quintile (treated as ordered categorical variable)
- Ethnicity (Categories: White, Black, Asian, Mixed, Other)
- Health Check questionnaire responses regarding:
 - Housing concerns
 - Enough food for family

- Struggle to pay bills
- Parental mental health concerns

Outcomes: Health service use rates, PedsQL, CHU9D, ACT, POEM, Constipation, WEMWBS, SDQ, school/work absence

These will be explored with separate models, each model including one measure of disadvantage, as we expect these measures of disadvantage to be highly correlated. However, for ethnicity and parental mental health concerns, we plan to also adjust for socioeconomic status, to assess if there is an additional effect of these factors beyond their correlation with socioeconomic status, using IMD, IDACI, and/or a Health Check measure.

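### The primary parent outcome (WEMWBS) has no rule for a carer with several enrolled children; standard errors are too small under the 11.10 fallback, the section 15 interactions and the 11.8 chi-squared tests

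*SAP*

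**What the plan says.** - **Outcome.** SAP 9.3 names "Warwick Edinburgh Mental Wellbeing scale (main carer) (Primary Parent Outcome". Section 11.3 scores it from the carer's own 14 items.
- **Who enters.** Section 3 takes "all children with asthma, eczema, or constipation who have consented for additional data collection and associated data linkage". Section 8.4 sets the child's age, the child's registration and "Parental informed consent confirmed". Neither section mentions siblings or a limit per family.
- **How it is collected.** Table 1 in 6.4 marks WEMWBS as collected on all participants, and 5.1 counts participants as children (1006 per arm).
- **Model.** Section 11.9 gives one model for all questionnaire outcomes: "Random-effects regression models. Covariates at individual level: participant age group, sex", then deprivation, borough and the baseline score. Section 11.10 says the random effects are there "to account for clustering by randomised GP cluster", and allows standard regression instead when correlation within clusters is minimal. It sets no threshold for minimal.
- **Other uses.** Section 15 tests effect modification by "adding an interaction term between measures of social disadvantage" and study arm, with WEMWBS and work absence among the outcomes. Section 11.8 analyses binary absence by logistic regression and also by chi-squared tests.
- **Identifier.** Section 6.5 describes only a patient ID built from the NHS number. No carer or family identifier is described.

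**The concern.** Asthma, eczema and constipation are common enough that one family may have two or three eligible children. The covariates in 11.9 are the child's age group and sex, so the natural reading is one row per child, with the carer's score attached to each. A carer with two enrolled children then supplies two nearly identical rows. The second row adds little information, but a method that treats rows as independent counts it in full.

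Two things are at stake. One is the standard error wherever the GP-cluster term does not absorb the repetition. The other is what is estimated: carers with several enrolled children count several times in an outcome defined on the parent. No variance correction changes that weighting, so the plan has to state the unit.

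**Working it through.** **1. Number of rows, from the plan's own sample size.** Section 5.1 gives 11 clusters per arm, a difference of 4.5, SD 16.5, 90% power, ICC 0.02 and 30% loss. A two-sided 5% level is assumed, because 5.1 states none. With t quantiles on 20 df, the size before clustering is (2.086 + 1.325)² × 2 × (16.5/4.5)² ≈ 313 per arm. With 11 clusters it is 313 × 0.98 / (1 − 313 × 0.02/11) ≈ 711, and 711/0.70 ≈ 1016. That is close to the stated 1006. So about 1006 × 0.70 ≈ 704 rows per arm are analysed. This calculation is for PedsQL. The SAP gives no sample size for WEMWBS and no sibling share.

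**2. Design effect from repeated carers.** Suppose a fraction f of carers have two enrolled children and the rest have one, and let ρ be the correlation between two rows of the same carer. Per carer, the mean of k is 1 + f and the mean of k² is 1 + 3f. The design effect is D = 1 + [(1 + 3f)/(1 + f) − 1]ρ. A test that ignores the repetition has true error 2[1 − Φ(1.96/√D)]. Both f and ρ are assumptions.

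| f | ρ | D | true SE / reported SE | true error at nominal 5% | distinct carers in 704 rows |
|---|---|---|---|---|---|
| 10% | 1.0 | 1.182 | 1.087 | 7.1% | 640 |
| 10% | 0.95 | 1.173 | 1.083 | 7.0% | 640 |
| 10% | 0.5 | 1.091 | 1.044 | 6.1% | 640 |
| 20% | 1.0 | 1.333 | 1.155 | 9.0% | 587 |
| 20% | 0.95 | 1.317 | 1.147 | 8.8% | 587 |
| 20% | 0.5 | 1.167 | 1.080 | 7.0% | 587 |

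**3. Arm effect: fallback against planned model.** Null simulation with 23 clusters of about 64 rows, siblings in the same cluster, identical carer scores, no covariates and 1500 runs per scenario. It adds families with three enrolled children. Entries are rejection rates at nominal 5%.

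| Carers with 2 / 3 children | ICC | Standard regression | GP-cluster random intercept, t on 21 df |
|---|---|---|---|
| none | 0 | 5.4% | 3.7% |
| 10% / 2% | 0 | 8.9% | 4.8% |
| 20% / 5% | 0 | 11.5% | 4.8% |
| none | 0.02 | 21.9% | 4.6% |
| 10% / 2% | 0.02 | 24.5% | 6.0% |
| 20% / 5% | 0.02 | 23.6% | 5.3% |

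In the 20% / 5% scenario the random-intercept SE averages 0.0652 against an empirical SD of 0.0653 at ICC 0, and 0.0879 against 0.0883 at ICC 0.02. The standard-regression SE stays near 0.053. Arm is assigned by cluster and siblings share a cluster, so the cluster term absorbs the repetition. At ICC 0.02, nearly all the excess error of standard regression comes from ignoring the GP cluster, not from siblings.

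**4. Equity interactions.** An interaction of arm with a household measure is largely a within-cluster contrast, and siblings share the measure. A GP-cluster intercept therefore does not absorb the repetition. In a simulation with clusters fully accounted for and ρ = 0.95, the interaction test rejected 6.2%, 7.1% and 8.2% of the time when 10%, 20% and 30% of rows shared a carer. The formula in step 2 gives 6.1%, 7.2% and 8.4% for the same inputs, so it applies here too. On that scale, f = 10% means 2 × 0.10/1.10 = 18% of rows, and f = 20% means 2 × 0.20/1.20 = 33%.

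**5. Work absence.** A plain chi-squared test has neither a cluster term nor a family term, so it treats siblings' rows as independent whatever 11.10 decides. The item asks about work missed because of that child, so siblings' answers can differ. Their correlation is unknown and probably lower than for WEMWBS.

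**The case against.** - **Child rows are inferred.** Nothing in 9.3, 11.3 or 11.9 states the row unit for WEMWBS, and nothing says that siblings were enrolled. The protocol or the data management plan may limit enrolment. This stands as a limit on certainty. But the unit and dependence structure of a primary outcome belong in the SAP, and 8.4 restates the entry criteria without a limit.
- **Intervals too narrow throughout.** A reader might infer this from the repeated rows. The documents do not support it: 11.9 plans random-effects models, and with the GP-cluster term kept and few-cluster inference the arm-effect interval is approximately valid (working, step 3).
- **The fallback is a fault of 11.10, not of WEMWBS.** This is partly right, since keeping the cluster term repairs the arm effect for every outcome. It does not repair the interactions or settle the weighting.
- **The correlation may be well below 0.95.** Siblings may complete forms at different times, and the model adjusts for baseline score. This stands; at 0.5 the error is about 6% to 7%.
- **One row per carer would be wrong for work absence.** This stands, because the item is specific to the child. Dropping siblings there would discard valid data.
- **The section 15 analyses are exploratory.** This stands and limits the weight of that part. IMD and IDACI are also area measures (13.2), and a family term does not address neighbours who share them.
- **Weighting by child is a legitimate choice.** It is, if it is stated.

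**Conclusion.** The point holds in limited form. A carer-level primary outcome sits in a child-level dataset with no carer unit, no sibling rule and no family level. For the planned arm comparison with the GP-cluster random effect kept, no material error in the interval is shown. Standard errors are too small under the 11.10 fallback, in the section 15 interactions on family-shared measures, and in the chi-squared tests of work absence.

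For WEMWBS, if 10% to 20% of carers have two enrolled children and their scores are nearly identical, a nominal 5% test has a true error of roughly 7% to 9%. The true SE is then about 8% to 15% larger than reported. The fallback figure takes a true GP-cluster ICC of zero. All of this rests on an assumed sibling share and on siblings being in the same GP cluster. If few siblings were enrolled, the effect is small. The extra weight given to carers with several enrolled children arises under any of these models.

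**What to change.** - **11.3 and 11.9, WEMWBS:** analyse one record per carer (the first child consented). Alternatively, keep all rows with family-robust variance or a family random intercept nested in the GP cluster, and state that carers are then weighted by their number of enrolled children. With mostly single-child families and near-identical scores, a family intercept may fit poorly, and one record per carer is simpler.
- **11.8, 11.9 and 15:** for work absence, parent-reported child outcomes and the equity interactions, keep all child rows and use the family-robust variance or family term. Do not rest the absence result on the plain chi-squared test.
- **11.10:** keep the GP-cluster term whatever the observed ICC, with few-cluster inference.
- **6.5 and 21:** derive a pseudonymised family ID from the consent or portal record, and report the number of distinct carers.

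The cost is a few sentences and one extra linking variable. That variable has to be created, because 6.5 describes only a patient ID. Intervals become slightly wider, and with one record per carer some duplicate WEMWBS rows are dropped.

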9.4 Primary care quality measures

Asthma

1. Proportion of CYP aged 5 years and over with asthma have a recorded personalised action plan.
2. Proportion of CYP aged 5 years and over with asthma have asthma review over a 12-month period.

3. Proportion of CYP aged 5 years and over with asthma have asthma control monitored at their asthma review.
4. Proportion of CYP aged 5 years and over with asthma have documented height at their asthma review.
5. Proportion of CYP who receive treatment in an emergency care setting for an asthma attack are followed up by their GP within 30 working days of discharge.
6. Proportion of CYP with asthma prescribed a spacer
7. Proportion of CYP with asthma have psychosocial assessment in addition to physical severity

Constipation

1. Proportion of CYP with diagnosed constipation receive oral macrogols as first-line treatment.
2. Proportion of CYP starting maintenance therapy have their first treatment review by a healthcare professional within 6 weeks.
3. Proportion of CYP with asthma have psychosocial assessment in addition to physical severity

Eczema

1. Proportion of CYP with atopic eczema are offered treatment based on recorded eczema severity.
2. Proportion of CYP with atopic eczema are prescribed sufficient quantities (250–500 g weekly) from a choice of unperfumed emollients for daily use.
3. Proportion of CYP of children with atopic eczema who have a repeat prescription of moderate/very potent topical steroids
4. Proportion of CYP with atopic eczema have psychosocial assessment at every eczema consultation.

10. HEALTH SERVICE USE OUTCOME DEFINITIONS AND ANALYSIS METHODS

10.1 Non-elective hospital admission (NEA) rates (Primary population outcome)

We will determine non-elective admissions from admitted care data, of CYP aged <16 years, registered with Lambeth and Southwark GP practices, admitted to St Thomas's, Guy's or King's College Hospitals. Admitted patient care is recorded in episodes. An episode is a record of an individual patient's care with a single consultant, within a hospital provider, and forms all or part of an overall hospital spell (an admission). Each episode contains data on the patient (age, area of residence and registered GP practice code); on the episode of care (the date of admission and method of admission - whether the admission was elective or non-elective); and clinical information. Diagnoses for each patient are recorded using the International Classification of Diseases, 10th edition (ICD-10) and the information is divided into the primary diagnosis (main problem treated) and various secondary diagnoses (including comorbidities and complications). Procedures performed during an episode are coded using the Office of Population, Censuses and Surveys Classification of Surgical Operations and Procedures, 4th revision (OPCS4).

We will select the dominant episode record for each admission and check for duplicate data using a combination of patient ID (pseudonymised) and admission date. We will calculate length of stay (days) as the date of discharge–date of admission.

A non-elective admission is an unplanned event and occurs when a consulting clinician determines a child's presenting condition is serious and requires immediate hospital care. Children who have well managed health conditions are less likely to experience a non-elective admission.

A non-elective admission is determined in Admission Method field as codes 21-25, 2A, 2B, 2D, 28. (See table in Appendix.)

NEA rates

Non-elective hospital admission (NEA) rate will be measured as number of events per patient-year in each GP practice.

The numerator is the number of NEA per GP practice and denominator is person-years of GP registered population under age 16. The numerator will be taken from GSTT and KCH data.

The denominator will be calculated from the Primary Care data extracts of individual level data, as these allow us to determine the 'time at risk' (i.e. time under observation per participant). Using these data, we can also access individual patient-level covariates (i.e. we can adjust for age, sex, IMD and IDACI score per patient, as described in section 15). This approach will be used for all rate-based outcomes.

Alternatively, the denominator could come from NHS Digital "Patients Registered at a GP Practice" but these data do not include patient-level covariates. Therefore we have decided to use the Primary Care data to estimate the observed number of patient-years.

10.2 Primary care (GP and nurse consultations)

A primary care consultation is a health contact between a primary care clinician and a child/young person.

Data

The primary care consultations will be extracted from Lambeth and Southwark primary care administrative systems (EMIS). Extractions will take place every quarter (3 months). See Data and reporting guidelines document for more details.

Consultation type

A contact can be face-to-face or via telephone, text or video. A contact can be in the practice surgery, out of hours or in another location such as the child's home. Consultation types that will be included in our count of consultations are listed in Appendix. Note that the listing of consultation types may not be exhaustive. If additional types are identified in the data set, a decision will need to be made on inclusion/exclusion prior to unblinding.

Staff roles

A consultation with a primary care clinician can be with a GP, nurse or other health care provider. Staff roles that will be included are listed in Appendix.

Primary care consultation definition and rates

Only consultations that meet both criteria will be included in our definition of a primary care consultation: a) the consultation type is for a consultation between a CYP and a clinician (see Appendix), and b) the staff role is meets our definition (see Appendix) for a primary care clinician.

The rate of primary care consultation rates will be measured as count per patient-year. Numerator (count) and denominators (population) will change depending on the evaluation analysis.

10.3 Outpatient appointment referrals from primary care

An outpatient appointment referral occurs when a primary care clinician decides a child needs specialist care. These referrals are recorded in EMIS as Read/SNOMED codes.

Outpatient appointment referral rates

The rate of Outpatient appointment referral rates will be measured as count per patient-year.

10.3.1 Referral to General Paediatrics

These are defined using the terms in Appendix. This outcome will be used for the “Health Service Use Population-level population” (as defined in section 8.1).

10.3.2 Referral to General Paediatrics and Tertiary services related to the tracer conditions

Rationale: If CYPHP is improving health, or through offering early intervention for asthma/eczema/constipation, we hypothesize there will be fewer tertiary service referrals for these conditions, as well as fewer referrals to general paediatrics. Referrals related to the tracer conditions are defined in Appendix. This outcome will include the referrals to General Paediatrics (defined in 10.3.1), and in the terms relevant to tracer conditions, listed in Appendix. This outcome will be used for “Health Service Use Population-level population” (as defined in section 8.1).

